3 STUDY OBJECTIVES AND ENDPOINTS

3.1 *Study Objectives*

3.1.1 *Primary Objective*

The data generated in this companion study will be used to demonstrate the ability of the MBT to evaluate patient response to treatment with BMS-986036, comparing placebo to each treatment arm individually. Primary efficacy assessment will be performed using the Week 24 and the Week 48 visit measures compared to Day 1 (change from baseline) for the combined population of the two cohorts, according to availability, by dose of the BMS drug under study.

The same assessments for each study cohort independently will be reported.

3.1.2 *Secondary Objective*

The following assessments will be done by treatment arm by dose of the BMS drug under clinical investigation and combined arms on the combined population of the two study cohorts:

1. To demonstrate the short and long-term prognostic value (3 months, 6 months and 1 year, respectively) of MBT for liver disease deterioration (reported as liver-related

Meridian Bioscience Israel Ltd.	Last update: May 05, 2021
SAP for Protocol BMS-EX-0118: Companion protocol for the ¹³C-Methacetin Breath Test (MBT) for use in Bristol-Myers Squibb phase 2b studies for BMS-986036 (PEG-FGF21), under Protocols MB130-068 and MB130-069	Document Version: 1.0
Document Nº: CSD00114	Page 9 of 21

clinical outcome events). Assessment will be performed using MBT from the Day 1, Week 24 and Week 48 visits.

2. To assess the ability of changes in the MBT to reflect biopsy proven changes in fibrosis and/or NAS as assessed by a central reader, where available, at Week 24 (or at least Week 20 in cases of an Early Termination time point) (for cohort 1) or at Week 48 (for cohort 2) compared to the baseline biopsy from the screening visit.
3. To assess the ability of changes in the MBT to reflect changes in liver stiffness as measured by Magnetic Resonance Elastography (MRE), where available, at Week 24 and Week 48 (or at Early Termination) compared to baseline MRE from the screening visit.
4. To assess the ability of changes in the MBT to reflect changes in Proton Density Fat Fraction (PDFF) as measured by Magnetic Resonance Imaging (MRI), where available, at Week 24 and Week 48 (or Early Termination), compared to baseline MRI from the screening visit.

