5. To assess the ability of changes in the MBT to reflect changes in Serum Pro-C3, where available, at Week 24 and Week 48 of treatment (or Early Termination), compared to baseline Pro-C3 from the screening visit.

The same assessments for each study cohort independently will be reported.

The following additional objectives are applicable for cohort 2 only:

1. To assess the ability of changes in the MBT to reflect changes in liver stiffness as measured by “Fibroscan” elastography, where available, at the Week 48 visit (or earlier if there was an Early Termination) compared to the screening visit.
2. To assess the ability of changes in the MBT to reflect changes in the Model for End-stage Liver Disease (MELD) score, where available, at Week 24 and Week 48 visits compared to study Day 1.
3. To assess the ability of changes in the MBT to reflect changes in the Child-Turcotte-Pugh Scoring (CTP) score, where available, at Week 24 and Week 48 (or Early Termination) compared to study Day 1.

Meridian Bioscience Israel Ltd.	Last update: May 05, 2021 Document Version: 1.0
SAP for Protocol BMS-EX-0118: Companion protocol for the ¹³C-Methacetin Breath Test (MBT) for use in Bristol-Myers Squibb phase 2b studies for BMS-986036 (PEG-FGF21), under Protocols MB130-068 and MB130-069	
Document Nº: CSD00114	Page 10 of 21

3.1.3 *Exploratory Objective*

- To assess the ability of the MBT to monitor patient status in comparison to other available measures, such as Liver Fibrosis stage, NAS, MELD, CTP, PDFF, Liver Stiffness, Serum Biomarker or Pro-C3.

3.1.4 *Safety Objective*

Evaluation of safety related to the MBT.

3.2 *Study Endpoints*

3.2.1 *Primary Endpoint*

The MBT's ability to measure the effect of BMS-986036 treatment on the metabolic capacity of the liver at Week 24 and Week 48 visits during the Double-Blind Treatment Period, as compared to changes in placebo treated subjects.

3.2.2 *Secondary Endpoints*

In order to assess the correlation of changes in MBT with changes in other measures of liver disease, the following endpoint measures will be collected, where available:

For all study cohorts: MBT results for each MBT visit (Day 1, Week 24, Week 48, or Early Termination visits) as well as changes in MBT results (cPDR₃₀, PDR_{peak} or other breath test parameters).

The other measures of liver disease that will also be collected in this study are as follows:

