The last dose of study medication will be at the Week 48 visit. Subjects will have a safety and efficacy evaluation at week 48 and return for a post-treatment follow-up evaluation through Week 52.

As a sub-study of BMS protocols MB130-068 and MB130-069, MBT will be performed at the Day 1 visit and every 24 weeks during the Double-Blind Treatment Period in order to allow the assessment whether BMS-986036 compared to placebo improves liver metabolic function as determined by the MBT.

4.1 *Sample Size Considerations*

Subjects, that were enrolled into two separate BMS sponsored IND studies (MB130-068, MB130-069, respectively) at selected study sites, were offered the opportunity to perform the MBT, and are considered as two separate study cohorts (cohort 1 and 2, respectively) for this companion protocol. Each cohort consists of four treatment arms (BMS-986036 10mg, 20mg, 40mg QW or matching placebo QW) as defined in the respective BMS sponsored protocols.

Cohort 1 consists of subjects with NASH and stage 3 fibrosis, as assessed by a central laboratory reader of the liver biopsies, and who meet all the MB130-068 study criteria. The sample size for this MB130-068 study is n=160.

Cohort 2 consists of subjects with NASH and compensated liver cirrhosis (stage 4 fibrosis) as assessed by a central laboratory reader of the liver biopsies, and who meet all the MB130-069 study criteria. The sample size for this MB130-069 study is n=100.

This feasibility companion protocol includes those two cohorts of subjects, which were planned for up to 260 subjects) from approximately 75 sites worldwide (USA and Japan) for the two BMS IND studies, while the MBT was only conducted in the USA.

It was expected that not all participating sites would elect to perform the MBT. The total number of subjects expected to perform the MBT was initially planned for up to 250 subjects (also accounting for drop outs). Each subject would perform up to 3 MBTs over 1 year.

Meridian Bioscience Israel Ltd.	Last update: May 05, 2021
SAP for Protocol BMS-EX-0118: Companion protocol for the ¹³C-Methacetin Breath Test (MBT) for use in Bristol-Myers Squibb phase 2b studies for BMS-986036 (PEG-FGF21), under Protocols MB130-068 and MB130-069	Document Version: 1.0
Document Nº: CSD00114	Page 13 of 21

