SAP for Protocol BMS-EX-0118: Companion protocol for the ¹³C-Methacetin Breath Test (MBT) for use in Bristol-Myers Squibb phase 2b studies for BMS-986036 (PEG-FGF21), under Protocols MB130-068 and MB130-069	Document Version: 1.0
Document Nº: CSD00114	Page 17 of 21

Day 1 MBT date plus 1). Subjects will be censored at their last study visit for the following reasons:

- If a subject discontinues the study prior to the end of the study without experiencing an event
- If a subject reaches the Final Treatment visit without experiencing an event

Survival analysis will be conducted using the Cox proportional hazard model. The model summary will include the number of subjects in the model, and a table with each covariate in a separate line specifying the coefficient's value, Hazard Ratio, Hazard Ratio 95% Confidence Interval and p-value. In addition, a Kaplan-Meier plot for event-free survival will be presented, stratified by MBT parameter along with the MBT parameter log-rank p-value. Additionally, a crosstab table of MBT parameter and events will be presented.

8.4.2.2 Correlations between changes in MBT parameters and changes in other liver related parameters

Repeat MBT results (cPDR₃₀, PDR_{peak} or other breath test parameters) and their changes in subjects with and without treatment (BMS-986036) for nonalcoholic steatohepatitis (NASH) at Day 1, Week 24 and Week 48 (or Early Termination visits) will be compared and tested for correlation to baseline, as well as repeat results (change from baseline), for the following measurements:

- a. Biopsy based Fibrosis and/or NAS score
- b. Liver stiffness as measured by MRE
- c. PDFF as measured by MRI
- d. Serum Pro-C3 results
- e. Liver elastography by Fibroscan (in cohort 2 only)
- f. MELD scores (in cohort 2 only)
- g. CTP scores (in cohort 2 only)

Linear Regression will be applied in order to test for significance of the correlations between MBT and the liver measurements listed above.

Changes in MBT are measured as the difference between baseline and each of the MBT visits as well as the change in measurements between two subsequent visits in each of the two treatment groups.

Meridian Bioscience Israel Ltd.	Last update: May 05, 2021
SAP for Protocol BMS-EX-0118: Companion protocol for the ¹³C-Methacetin Breath Test (MBT) for use in Bristol-Myers Squibb phase 2b studies for BMS-986036 (PEG-FGF21), under Protocols MB130-068 and MB130-069	Document Version: 1.0
Document Nº: CSD00114	Page 18 of 21

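### For biopsy, MRE, PDFF and Pro-C3, the combined-cohort regressions in SAP 8.4.2.2 have no cohort term, so their slope and nominal p-value can reflect differences between the cohorts.

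*SAP*

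**What the plan says.** SAP 3.1.2 places the secondary assessments, by arm and for "combined arms on the combined population of the two study cohorts", and then adds: "The same assessments for each study cohort independently will be reported". It does not say which result governs interpretation.

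SAP 8.4.2.2 lists seven liver measures. MBT results and changes "will be compared and tested for correlation to baseline, as well as repeat results (change from baseline"), and the model is stated only as: "Linear Regression will be applied in order to test for significance of the correlations between MBT and the liver measurements listed above". No covariates are given. Items a-d (biopsy fibrosis and/or NAS, MRE, PDFF, Pro-C3) apply to both cohorts. Items e-g (Fibroscan, MELD, CTP) are restricted to cohort 2.

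Biopsy change is taken "at Week 24 (or at least Week 20 in cases of an Early Termination time point) (for cohort 1) or at Week 48", the later time being that of cohort 2. On entry stage, SAP 4.1 says "Cohort 1 consists of subjects with NASH and stage 3 fibrosis", while cohort 2 has compensated cirrhosis, stage 4. Protocol 7.7.1.1 stages fibrosis from 0 to 4.

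SAP 8.5 adds a site by dichotomised-MBT interaction to the linear models and groups small sites within each cohort. SAP 6.1 makes all analyses descriptive, with nominal p-values.

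**The concern.** The scientific question is whether MBT moves with liver disease within patients. If the cohorts have different mean MBT values or changes and also different mean liver-measure values or changes, a pooled line runs partly between the two cohort means. It can then show an association that exists in neither cohort. If the two differences have opposite signs, it can show a false negative association or hide a real positive one.

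The cohorts are not exchangeable on these measures. Cohort 2 starts at the top of the fibrosis scale and cannot worsen on it, whereas cohort 1 can. Biopsy change covers 24 weeks in one cohort and 48 in the other, so interval is completely confounded with cohort in a combined biopsy regression. Baseline fibrosis stage is fixed at 3 or 4 by cohort, so a pooled regression on it compares cohorts and nothing else.

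At stake is the reading of the combined results on whether MBT reflects liver change, from data that SAP 4 says may be used for future submissions.

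**Working it through.** **Figure to reproduce.** The documents give no expected correlation, SD or power for these regressions. The only related arithmetic is the parent-study total, 160 + 100 = 260, which agrees.

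**Inputs from the documents.** Fewer than 80 subjects with valid baseline and post-treatment MBT (SAP 2 and 4.1); parent-study sizes 160 and 100 (SAP 4.1); two-sided nominal 5% level (SAP 8.1).

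**Assumptions, not in the documents.** N = 79, 75 or 40; cohort 2 share p = 100/260, or 1/2 as an alternative; zero correlation within each cohort; mean shifts between cohorts of dx (MBT) and dy (liver measure), in within-cohort SD units.

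**Induced correlation.** With q = p(1 - p),

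r = q·dx·dy / √[(1 + q·dx²)(1 + q·dy²)].

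For p = 100/260, q = 0.3846 × 0.6154 = 0.2367. With dx = dy = d this reduces to r = q·d²/(1 + q·d²):

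- d = 0.3: 0.0213/1.0213 = 0.02
- d = 0.5: 0.0592/1.0592 = 0.06
- d = 0.8: 0.1515/1.1515 = 0.13
- d = 1.0: 0.2367/1.2367 = 0.19

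**Rejection rate of the nominal 5% slope test** (20,000 simulated datasets per setting, p = 100/260):

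| Shift in both variables (SD) | N = 79, no cohort term | N = 79, cohort term | N = 40, no cohort term |
|---|---|---|---|
| 0 | 5.0% | 5.0% | 5.2% |
| 0.3 | 5.1% | 4.7% | 5.2% |
| 0.5 | 7.6% | 4.9% | 6.2% |
| 0.8 | 20.9% | 4.9% | 12.8% |
| 1.0 | 40.2% | 5.0% | 21.6% |

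With a 1:1 split, N = 79 and 1.0 SD, the rate without a cohort term is 43.3%. Across all settings tried, the rate with a cohort term lay between 4.7% and 5.2%.

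**Unequal shifts** (N = 75, split 46:29, 40,000 datasets). The rate is about 5% at 0.5 and 0.2 SD, 6% at 0.8 and 0.2, and 8% at 1.0 and 0.3. A large shift in one variable does little unless the other shifts as well.

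**Baseline fibrosis stage.** Stage equals 3 in cohort 1 and 4 in cohort 2, so the pooled regression of MBT on stage is algebraically the two-sample comparison of cohorts. In a simulated check both gave p = 0.1066. At N = 79 (49:30) it would be nominally significant with probability 25%, 58% or 93% if mean MBT differed by 0.3, 0.5 or 0.8 SD. Within a cohort the predictor is constant and the slope is undefined.

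**The case against.** The strongest reply is that the SAP also reports each cohort separately. Those regressions carry no cohort confounding, so a reader can see whether a pooled slope survives. The order of the text does not establish that the combined result takes precedence. This stands as mitigation, but the combined estimate is still produced and remains uncorrected.

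Second, the size needs sizeable shifts in both variables. Cohorts that differ in disease level need not differ much in change, and nothing in the documents says they do. This stands: at about 0.3 SD the effect is negligible.

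Third, SAP 8.5 might absorb the cohort difference. Site main effects coded uniquely by cohort could do so, but the SAP states only an interaction for the linear models and does not say that group labels are unique across cohorts.

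Fourth, everything is descriptive. Rejection rates therefore measure distortion here, not loss of a controlled error rate. A confounded slope misleads as a description too.

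A reader might also infer three stronger points that the documents do not support:

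- **All seven measures are affected.** Items e-g are cohort 2 only, and the mixing of 24 and 48 weeks concerns biopsy alone.
- **Week 24 and Week 48 rows from one subject will be stacked as independent.** The SAP does not say so. It defines changes to each visit, and by-visit fitting is the natural reading.
- **Biopsies lack a matching MBT.** Protocol 10.2 schedules the MBT at Weeks 24 and 48, ahead of any biopsy, so a same-visit MBT is planned. What is missing is an analysis rule that uses it.

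A rank correlation for the ordinal scores would be a useful clarification; its absence is not an error.

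**Conclusion.** The concern holds for the combined-cohort regressions of items a-d. With no cohort term, the slope and nominal p-value mix the within-cohort association with a cohort contrast that is built into the design through stage, scale ceiling and, for biopsy, interval.

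The size cannot be fixed from the documents. It is negligible when the cohorts differ by about 0.3 SD or less in both variables, or substantially in only one. It is material from about 0.8 SD in both (about 21% nominal rejection at N = 79, and 13% at N = 40). These figures assume no within-cohort correlation and equal shifts in the same direction. The cohort-specific results and the descriptive status limit the consequence but do not remove the defect. The pooled baseline-stage regression is legitimate as a contrast of stage 3 with stage 4, but not as evidence that MBT tracks fibrosis within a stage.

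The interval point takes cohort 1 biopsy at Week 24, as in SAP 3.1.2 and Protocol 7.7 and 7.7.1. Protocol 9.6.5 describes 48 weeks of follow-up before biopsy in connection with cohort 1, and these passages must be reconciled. The stage and ceiling differences do not depend on that.

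**What to change.** In SAP 8.4.2.2:

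1. Add cohort as a covariate in every combined-population linear regression for items a-d, and report the within-cohort (partial) association as the combined estimate.
2. For biopsy, regress on the MBT change over the same interval as the biopsy change, and state that interpretation rests on the cohort-specific results.
3. Describe the pooled regression on baseline fibrosis stage as a comparison of stage 3 with stage 4 cohorts only, and omit it within cohort.
4. As clarifications, state that each visit is fitted separately (or use a subject random effect if visits are combined), and say whether a rank correlation will accompany the linear fit for ordinal scores.

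The cost is one degree of freedom per model, SAP wording and slightly more programming. SAP 2 allows amendment before the company accesses the released data.

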8.5 Site Poolability

Primary efficacy analysis will be reported for each cohort separately as well as for each site/group of sites (see next section) separately.

For sites with less than 10 subjects, the following pooling of sites method will be applied for each cohort separately: Sites will be sorted from smallest to largest based on the number of randomized subjects with valid baseline MBT results. The smallest site will be pooled with the second smallest, and if necessary with the next sites in line until the site group reaches 10 subjects or more. The site value for those sites will be assigned "Site Group 1". Then the next site in line, if lower than 10 subjects, will be pooled with the sites after it until the site group reaches at least 10, and so forth until all sites or site groups have at least 10 subjects. Furthermore, site by MBT dichotomy interaction will be added to the Linear and Cox regression models as a covariate to test for site effect on the exploratory endpoints.

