9.6.6 Pooling

As there will be very few subjects enrolled at any given site, data from all sites will be pooled for analyses for each study cohort separately and combined cohorts.

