Only trained personnel will perform the breath test procedure. The actual breath collection is automatically performed by the device and is not operator dependent. If the IDcircuit (a nasal cannula manufactured specifically for Exalenz) is not connected properly to the subject (e.g. the breath does not reach the device), the BreathID® MCS device will prompt the operator to adjust the IDcircuit.

1. Turn on the device from the switch in the rear and allow up to 1 hour for warm-up to complete. To perform the test, ensure that the BreathID® MCS screen shows that the device is in 'Ready' state.
2. The IDcircuit will be attached to the BreathID® MCS device and to the patient. Pressing the "Start" button on the device will begin the collection of the patient's baseline exhaled breath. This will take approximately 5-10 minutes.
3. The ¹³C-Methacetin solution is poured into a disposable cup and administrated to the patient when prompted by the device. The solution should be administered by a medical practitioner registered on the delegation log or a research nurse if specific training for administration has been given. Immediately after ingestion, the operator will press the "Continue" button, which activates the actual measurement. CO₂ production with ¹³C may be visible within a few minutes in cases with relatively functional livers.

| | |
|---|---|
| Exalenz Bioscience Ltd. | Last update: February 20, 2018 |
| Study Title: Companion protocol for the ¹³C-Methacetin Breath Test (MBT) for use in Bristol-Myers Squibb phase 2b studies for BMS-986036 (PEG-FGF21), under Protocols MB130-068 and MB130-069 | Protocol: BMS-EX-0118 Version: 1.0 |
| Document No: CSP000002 | Page 35 of 38 |

Note: In rare cases, the administration of fluids may cause vomiting. If this happens, the test should be aborted and repeated on one of the subsequent days. The experienced adverse event should be reported in the appropriate CRF section.

4. The patient should remain in a seated position breathing in a normal manner for up to 85 minutes, while data is collected.
5. The BreathID® MCS device continuously measures and analyzes the patient's exhaled breath in real time. As the ¹³C-Methacetin is metabolized, the value of the ¹³CO₂/¹²CO₂ ratio in the exhaled breath will change and will be calculated in real time by the device.

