However, as aforementioned in the Introduction (section 2), the enrollment phase and all MBT testing (incl. Day1, Week 24 and Week 48 visits) for the aforementioned BMS sponsored studies has been completed. The data is still being assessed by BMS and the respective databases are planned to be made available to Exalenz between July and November 2021, after their respective data lock and release from BMS.

The initially planned sample size of 250 subjects, per statistical section in the companion protocol, was not reached for multiple reasons:

- The MBT testing as part of the BMS studies, was an opt in substudy, requiring an additional consent process. Subjects enrolled to the BMS studies were reluctant to add an additional investigational test to their study schedule.
- The COVID-19 outbreak further complicated the enrollment and especially the follow up testing of already enrolled subjects, as visits were more and more conducted remotely and any breath testing was avoided during in person visits.

Since the actual final sample size of subjects with valid MBT results at baseline and post-treatment phase, across both BMS studies, is expected to be lower than 80, the statistical analyses for the study will be descriptive by nature. No formal statistical testing will be performed. Nominal p-values from statistical tests will be reported for supplementary information.

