In order to show the ability of the MBT to measure the effect of BMS-986036 treatment on the metabolic capacity of the liver after Week 24 and Week 48 visits, as compared to changes in placebo treated subjects, the primary endpoint will be analyzed using a responder analysis, where any increase of MBT value will be considered as a response while a same value or a decrease of the MBT value will be considered as non-response.

The primary analysis will be conducted on the mEA set, with the PDR_{peak} and cPDR₃₀ responder rate of Week 24 and Week 48 of data from both BMS' studies.

Individual analyses for each cohort separately will also be reported.

8.4.2 *Secondary Endpoints*

8.4.2.1 *Prognostic Value of MBT in Overall Event-Free Survival*

In order to assess the prognostic value of MBT in prediction of liver disease deterioration (reported as liver-related clinical outcome events), the endpoint measures will be point estimates of Cox Regression's Hazard Ratio for classifying Subjects into risk groups for clinical deterioration with respective exact two-sided 95% confidence intervals in the placebo and treatment arms as determined by MBT. The MBT parameter to be used to predict liver-related clinical outcome events is PDR_{peak}. Any PDR_{peak} value of less or equal to 20 %/h (see **Appendix A** for detailed description of parameter calculation) will be considered as 'high risk' and any value above that threshold will be considered as 'lesser risk' (additional cut-off values may be explored). The dichotomic MBT result will be tested for significance using the Cox proportional hazards regression model with site and randomized arm as covariates. If the randomized arm factor is found non-significant (i.e. p-value > 0.05), then this factor will not be a covariate for the main analysis to be performed. If the randomized arm factor is found statistically significant (i.e. p-value ≤ 0.05), then the main analysis will be performed keeping this factor as a covariate (to 'adjust' the analysis for treatment).

The time-to-first event will be derived as the number of days between the Day 1 MBT test and the date when the first event occurs or when a subject is censored (i.e., event/censored date minus

Meridian Bioscience Israel Ltd.	Last update: May 05, 2021

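### The combined-cohort Cox model has no cohort term and SAP 8.5's site-group labels do not identify the cohort, so the MBT hazard ratio can absorb the cohort difference

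*SAP*

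**What the plan says.** - **Population.** SAP 3.1.2 puts the secondary assessments on the combined population of the two cohorts and also reports each cohort on its own.
- **Model.** In SAP 8.4.2.1 the dichotomised PDRpeak (20 %/h or less is high risk) is tested "using the Cox proportional hazards regression model with site and randomized arm as covariates". No cohort term or stratification is mentioned.
- **Site factor.** For sites with fewer than 10 subjects, SAP 8.5 states that "the following pooling of sites method will be applied for each cohort separately". Sites are ordered by size and merged until a group reaches 10. "The site value for those sites will be assigned" is followed by the name 'Site Group 1', and further groups are formed in the same way. Sites with 10 or more subjects keep their own value. SAP 8.5 also adds a site-by-MBT interaction to the linear and Cox models.
- **Size.** The number with valid baseline and post-treatment MBT, both studies together, "is expected to be lower than 80" (SAP 4.1). Protocol 9.6.6 opens with "As there will be very few subjects enrolled at any given site".
- **Cohorts.** Cohort 1 has stage 3 fibrosis and cohort 2 compensated cirrhosis. Protocol 3.2 links advanced disease with low MBT values. Protocol 7.7.2 evaluates liver-related outcome events in cohort 2, whereas SAP 3.2.2 lists them among the measures for all cohorts.

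**The concern.** MBT status is not randomised, so the hazard ratio is protected from cohort confounding only by what the model contains. The protocol's own text makes confounding plausible on both sides: the more advanced cohort is expected to have lower MBT values, and it is the cohort in which outcome events are evaluated.

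The site factor is the only term in the model that could separate the cohorts. If groups are numbered afresh within each cohort and the numbers are used as they stand, 'Site Group 1' in cohort 1 and 'Site Group 1' in cohort 2 become the same level. A comparison within that level is then partly a comparison of cirrhosis with stage 3 fibrosis.

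At stake are the hazard ratio, 95% interval and p-value behind the first secondary objective. The SAP calls its analyses descriptive, but it reports all three and says the data may be used for future submissions.

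**Working it through.** The documents give no event count, target hazard ratio or power for this model, so there is no stated figure to reproduce.

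**Inputs from the documents.** Fewer than 80 subjects (79 used as a ceiling). "The sample size for this MB130-068 study is n=160" and "The sample size for this MB130-069 study is n=100" are used only for the cohort split: 79 × 160/260 = 48.6 and 79 × 100/260 = 30.4, so 49 and 30 if opt-in was proportional. Minimum group size is 10.

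**Number of levels.** 49/10 allows at most 4 groups and 30/10 at most 3. Unique coding gives up to 7 levels (6 parameters). Repeated coding of the pooled groups gives up to 4 (3 parameters).

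**Assumptions, not in the documents.** Yearly hazards 0.12 (cohort 1) and 0.6 (cohort 2); high-risk share 30% and 60%; 18 and 12 MBT sites; true MBT hazard ratio 1.

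**Hand check of the mechanism.**

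1. With the cohorts not separated at all, the high-risk subjects are 49 × 0.3 = 14.7 from cohort 1 and 30 × 0.6 = 18 from cohort 2. The low-risk subjects are 34.3 and 12.
   - High-risk mean hazard: (14.7 × 0.12 + 18 × 0.6)/32.7 = 0.384.
   - Low-risk mean hazard: (34.3 × 0.12 + 12 × 0.6)/46.3 = 0.244.
   - Apparent hazard ratio: 0.384/0.244 = 1.57.
2. With repeated labels, the simulated pooling gave on average 3.95 distinct labels, against 6.01 when unique. That is about 4 groups in cohort 1 and 2 in cohort 2, so two labels are shared. They hold all 30 cohort 2 subjects and about half of cohort 1 (24.5).
   - High-risk: (7.35 × 0.12 + 18 × 0.6)/25.35 = 0.461.
   - Low-risk: (17.15 × 0.12 + 12 × 0.6)/29.15 = 0.318.
   - Ratio within shared labels: 1.45.
   - The cohort 1-only labels have ratio 1 and carry about 2.9 of 23.9 expected events per year. Event weighting gives exp(0.877 × ln 1.45) = 1.39.

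**Simulation.** The 8.5 pooling rule was coded and the Cox model fitted in 1,500 runs per setting, leaving out the arm covariate and the interaction to isolate the site factor. Bias is exp(mean error in log HR), for example exp(0.346) = 1.41. There was no added between-site variation in these rows.

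| Setting | Site coding | Bias in HR | 95% CI coverage | RMSE of log HR |
|---|---|---|---|---|
| Hazards 0.12/0.6, true HR 1 | no site factor | ×1.59 | 0.879 | 0.741 |
| | repeated labels | ×1.41 | 0.922 | 0.689 |
| | unique labels | ×0.99 | 0.955 | 0.627 |
| | cohort term only | ×0.99 | 0.960 | 0.590 |
| Same, true HR 2 | repeated labels | ×1.41 | 0.919 | 0.633 |
| | unique labels | ×1.05 | 0.955 | 0.561 |
| No events in cohort 1, true HR 1 | repeated labels | ×1.89 | 0.832 | 0.895 |
| | unique labels | ×1.00 | 0.956 | 0.653 |
| No cohort difference (0.4/0.4, 45% high risk in both), true HR 2 | repeated labels | ×1.04 | 0.949 | 0.439 |
| | unique labels | ×1.05 | 0.939 | 0.455 |

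A second simulation used other assumptions: 78 subjects (48/30), 8 or 12 events, 20% and 40% high risk, cohort hazard ratio 4, 500 runs per setting. Repeated labels gave a median HR of 1.3–1.4 when the truth was 1 and 3.7–3.8 when it was 3. A cohort-stratified model gave 1.0–1.1 and 2.9–3.0.

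**Cost of unique groups against a cohort term** (hazards 0.12/0.6). Mean SE: 0.591/0.575 = 1.03. Empirical SD: 0.627/0.590 = 1.06 at true HR 1 and 0.559/0.522 = 1.07 at true HR 2. The size-sorted groups captured about 22% of between-site variance with 18/12 sites, 19% at N = 60, and 62% with 5/3 sites.

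**The case against.** **The clash is inferred from silence.** SAP 8.5 gives one example name and does not say how groups are coded in a combined model. Groups formed separately may naturally be read as distinct, and a programmer may code them so. This stands: the defect follows from a literal reading and is not a certainty. The SAP should still say which coding applies, because nothing else in the model separates the cohorts.

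**The site factor is not itself the harm.** A reader might infer that the site groups damage the model and should be removed. The figures do not support that. When the cohorts differ, unique groups are nested in cohort and remove the bias, and they beat having no site factor (RMSE 0.627 against 0.741). Even repeated labels did better than none (0.689). What is missing is a cohort term.

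**Site is partly adjusted for.** Sites with 10 or more subjects enter directly, and the pooled groups capture some site variance. Protocol 10.2's "automatically performed by the device and is not operator dependent" describes breath collection, not the ascertainment of clinical events, so it does not show that site is irrelevant to this model.

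**The Cox sample size is not known.** The figure below 80 counts subjects with both baseline and post-treatment MBT. The Cox model starts at the Day 1 test and may include more. The simulated precision costs are therefore illustrative.

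**Consequences are limited.** P-values are nominal and each cohort is reported separately, so a cohort effect could be noticed. That tempers the point but does not correct the combined hazard ratio.

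**Conclusion.** The concern holds in a limited form. Followed literally, SAP 8.5 and 8.4.2.1 give a combined-cohort hazard ratio in which stage 3 and cirrhosis subjects share site levels and no term separates them. Inflation is about ×1.4 at a true hazard ratio of 1 in both simulations, and up to about ×1.9 if cohort 1 has no events. These sizes rest on assumed cohort differences in event risk and MBT. The bias vanishes if there are no such differences or if the labels are coded uniquely.

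It does not follow that site terms must go. Once cohort is accounted for, size-sorted groups add little when sites are tiny and cost about 3% in mean SE and 6–7% in empirical SD under the assumed inputs. Keeping or dropping them is a modelling trade-off.

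**What to change.** 1. In SAP 8.4.2.1, stratify the combined-cohort Cox model by cohort.
2. In SAP 8.5, make site-group values cohort-specific (for example 'C1 Site Group 1' and 'C2 Site Group 1') wherever a site factor enters a combined-cohort model, including the interaction and the linear regressions.
3. Optionally, show a cohort-stratified fit without site terms as a sensitivity analysis.

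The cost is a few lines of SAP text and code. SAP section 2 allows amendments before the sponsor accesses the data; after that, the change would be documented in the clinical study report. The drawback is that a cohort without events contributes nothing to the stratified estimate, so events should be reported by cohort beside it.
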